5.3.4 Electrocardiogram

Regular ECGs are to be conducted during the first year of the trial. Rate, rhythm and repolarisation changes have to be looked at, compared to previous one, and assessed for clinical relevance. Clinically relevant findings at baseline of this trial will be recorded as baseline conditions, new abnormal findings thereafter will be recorded as adverse events.

5.3.5 Other Safety parameters

Not applicable.

5.3.6 Assessment of adverse events

5.3.6.1 Definitions of adverse events

Adverse event

An adverse event (AE) is defined as any untoward medical occurrence, including an exacerbation of a pre-existing condition, in a patient in a clinical investigation who received a pharmaceutical product. The event does not necessarily have to have a causal relationship with this treatment.

Serious adverse event

A serious adverse event (SAE) is defined as any AE which results in death, is immediately life-threatening, results in persistent or significant disability / incapacity, requires or prolongs patient hospitalisation, is a congenital anomaly / birth defect, or is to be deemed serious for any other reason if it is an important medical event when based upon appropriate medical judgement which may jeopardise the patient and may require medical or surgical intervention to prevent one of the other outcomes listed in the above definitions.

Every new occurrence of cancer will be reported as a SAE regardless of the duration between discontinuation of the drug and the occurrence of the cancer.

Intensity of adverse event

The intensity of the AE should be judged based on the following:

Mild: Awareness of sign(s) or symptom(s) which is/are easily tolerated
Moderate: Enough discomfort to cause interference with usual activity
Severe: Incapacitating or causing inability to work or to perform usual activities

Causal relationship of adverse event

Medical judgment should be used to determine the relationship, considering all relevant factors, including pattern of reaction, temporal relationship, de-challenge or re-challenge,

Proprietary confidential information.

© 2017 Boehringer Ingelheim International GmbH or one or more of its affiliated companies. All rights reserved.

This document may not - in full or in part - be passed on, reproduced, published or otherwise used without prior written permission.

confounding factors such as concomitant medication, concomitant diseases and relevant history. Assessment of causal relationship should be recorded in the case report forms.

Additional information for Japan: The reason for the decision on causal relationship needs to be provided in the eCRF.

Yes: There is a reasonable causal relationship between the investigational product administered and the AE.

No: There is no reasonable causal relationship between the investigational product administered and the AE.

Worsening of the underlying disease or other pre-existing conditions

Worsening of the underlying disease or of other pre-existing conditions will be recorded as an (S)AE in the eCRF.

Changes in vital signs, ECG, physical examination, and laboratory test results

Changes in vital signs, ECG, physical examination and laboratory test results will be recorded as an (S)AE in the eCRF, if they are judged clinically relevant by the investigator.

Protocol-specified significant events

Similar to the parent trials, the following are considered as Protocol-specified significant events:

- Hepatic injury defined by an elevation of AST and/or ALT ≥ 3 fold ULN combined with an elevation of bilirubin ≥ 2 fold ULN measured in the same blood draw sample.

Patients showing these lab abnormalities need to be followed up according to [Section 10.1.1](#) of this clinical trial protocol and the “DILI checklist” provided in ISF.

- Adverse events relating to gastrointestinal perforation.

Protocol-specified significant events are to be reported in an expedited manner similar to Serious Adverse Events, even if they do not meet any of the seriousness criteria – for details please see [Section 5.3.7](#).

Expected Adverse Events

Expected (listed) AEs are described in Section 7.9 of the Investigator’s Brochure ([U07-1248](#)).

Proprietary confidential information.

© 2017 Boehringer Ingelheim International GmbH or one or more of its affiliated companies. All rights reserved.

This document may not - in full or in part - be passed on, reproduced, published or otherwise used without prior written permission.

5.3.7 Adverse event and serious adverse event reporting

All adverse events, serious and non-serious, occurring during the course of the clinical trial (i.e., from signing the informed consent onwards through the observational period of 28 days) will be collected, documented and reported to the sponsor by the investigator on the appropriate eCRFs / SAE reporting forms. Reporting will be done according to the specific definitions and instructions detailed in the ‘Adverse Event Reporting’ section of the Investigator Site File.

For each adverse event, the investigator will provide the onset date, end date, intensity, treatment required, outcome, seriousness, and action taken with the investigational drug. The investigator will determine the relationship of the investigational drug to all AEs as defined in [Section 5.3.6.1](#).

The investigator also has the responsibility to report AEs occurring in a certain period (28 days) after a patient completes the study drug administration. After this defined period all SAEs related to the study drug and/or study design have to be reported by the investigator.

The investigator must report the following events via telephone/fax using the SAE form immediately (within 24 hours or the next business day whichever is shorter) to the sponsor: SAEs and non-serious AEs occurring at the same time as an SAE and/or which are medically related to the SAE(s), and protocol-specified significant events.

Boehringer Ingelheim has set up a list of AEs which are defined to be always serious. In order to support the investigator with the identification of these “always serious adverse events”, if a non serious AE is identified to be serious per BI definition, a query will be raised. The investigator must verify the description and seriousness of the event. If the event description is correct, the item “serious” needs to be ticked and an SAE has to be reported in expedited fashion following the same procedure as above.

The list of these adverse events can be found in the ISF.

Additional information for Japan: This information must be also reported immediately to the head of the trial site.

With receipt of any further information to these events, a follow-up SAE report has to be provided. SAEs and non-serious AEs must include a causal relationship assessment made by the investigator.

The SAE form is to be forwarded to the defined unique entry point identified for the BI OPU (country-specific contact details will be provided in the Investigator Site File). This immediate report is required irrespective of whether the investigational product has been administered or not and irrespective of causal relationship. It also applies if new information to existing SAEs or protocol-specified significant events becomes available.

Pregnancy

As mentioned above, due to the reprotoxic potential of nintedanib, a patient must not become pregnant while treated with nintedanib and until 3 months after end of treatment.

Proprietary confidential information.

© 2017 Boehringer Ingelheim International GmbH or one or more of its affiliated companies. All rights reserved.

This document may not - in full or in part - be passed on, reproduced, published or otherwise used without prior written permission.

However, generally, in rare cases, pregnancy might occur in clinical trials. Once a female subject has been enrolled into the clinical trial, after having taken study medication, the investigator must report immediately any drug exposure during pregnancy to the sponsor. Drug exposure during pregnancy has to be reported immediately (within 24 hours or next business day whichever is shorter) to the defined unique entry point for SAE forms of the respective BI OPU (country-specific contact details will be provided in the Investigator Site File). The outcome of the pregnancy associated with the drug exposure during pregnancy must be followed up. In the absence of an (S)AE, only the Pregnancy Monitoring Form for Clinical Trials and not the SAE form is to be completed. The ISF will contain the Pregnancy Monitoring Form for Clinical Trials (Part A and Part B).

5.4 DRUG CONCENTRATION MEASUREMENTS AND PHARMACOKINETICS

Not applicable.

5.5 ASSESSMENT OF EXPLORATORY BIOMARKER(S)

Not applicable.

5.6 OTHER ASSESSMENTS

Not applicable.

5.7 APPROPRIATENESS OF MEASUREMENTS

The scheduled measurements are appropriate to see drug induced changes in vital signs, standard laboratory values and ECG. These endpoints are standard and accepted for evaluation of safety and tolerability of an oral drug, and they are widely used in this kind of study. The timing of all measurements is presented in the [Flow Chart](#).

Spirometry is a validated and well-established measurement tool for lung function testing ([P05-12782](#)).

6. INVESTIGATIONAL PLAN

6.1 VISIT SCHEDULE

All patients are to adhere to the visit schedule as specified in the [Flow Chart](#). Some flexibility is allowed in scheduling the visits according to visit time windows as specified in the Flow Chart. If any visit has to be rescheduled, subsequent visits should follow the original visit date schedule (calculated from Visit 2). The trial medication kits contain sufficient medication to allow for these time windows. All deviations from the planned visit schedule will be documented.

The trial will run until all patients have discontinued treatment or a stopping criterion is met according to [Section 3.3.4](#).

6.2 DETAILS OF TRIAL PROCEDURES AT SELECTED VISITS

6.2.1 Screening

The study will be explained to all patients who complete the parent trials and are willing to continue treatment with nintedanib. No study related procedure should be performed until the patient has signed the Informed Consent.

Patients will complete a 52 weeks treatment period with nintedanib (or placebo) at Visit 9 in the parent trial (1199.32 or 1199.34) and a follow-up period of at least 28 days without drug (Follow-up Visit).

After concluding all visits from the parent trial and in order to assess eligibility for the extension trial (1199.33), patients are required to perform a screening visit (Visit 1) which includes laboratory tests.

If the period between Visit 9 (End of Treatment) of the parent trial and the first visit of 1199.33 is ≤ 6 weeks, Visit 1 and Visit 2 may occur on the same date. In this case, eligibility assessment will be based on laboratory data from Visit 9 of the parent trial.

Please refer to the Flow Chart for complete procedures at Visit 1.

Patients who have a laboratory test value that is outside the range specified by the exclusion criteria may have the test repeated once to determine eligibility; however, the result must be available prior to Visit 2.

Details of any patient who has given informed consent for the trial but is found to be ineligible must be entered in the Enrolment log and documented in the eCRF.

Proprietary confidential information.

© 2017 Boehringer Ingelheim International GmbH or one or more of its affiliated companies. All rights reserved.

This document may not - in full or in part - be passed on, reproduced, published or otherwise used without prior written permission.

6.2.2 Treatment period

If the patient has been determined eligible by the investigator to enter the trial (refer to [Section 3.3](#)), the investigator will assign a medication number to the patient through IVRS/IWRS at Visit 2 (refer to [Section 4.1.2](#)). First dose of nintedanib will be administered at Visit 2 in the clinic (day 1).

Additional clinic visits will be scheduled after 2, 4, 6, 12, 24, 36 and 48 weeks of treatment (Visits 3-9). Liver function monitoring visits will be performed at 18, 30 and 42 weeks of treatment (Visits 6a, 7a and 8a). After the first year of treatment, complete clinic visits will be scheduled every 16 weeks with intermediate liver function monitoring visits.

For detailed description of the trial procedures at each visit and dispensing schedule, please refer to the [Flow Chart](#).

End of Treatment (EOT)

If a reason for drug discontinuation is met (refer to [Section 3.3.4](#)) an EOT Visit should be scheduled as soon as possible after last drug intake. Reason for discontinuation must be documented in the eCRF.

For detailed description of the trial procedures at the EOT visit, please refer to the Flow Chart.

6.2.3 End of trial and follow-up period

A Follow-up (FU) Visit should be planned for 28 days after last drug intake.

For detailed description of the trial procedures at the FU Visit, please refer to the Flow Chart.

If the reason for removal of a patient from the treatment is an adverse event or an abnormal laboratory test result, the patient must be followed until complete resolution or stabilization of the event for at least 28 days after onset of the event or until follow-up is considered adequate by the investigator and the clinical monitor.

A patient will be considered lost to follow-up if the investigator is not able to contact him/her despite multiple attempts. Every effort must be made; at least 2 telephone contacts plus 1 mailing should be documented. The site must notify the clinical monitor prior to designating a patient as lost to follow-up.

6.2.4 Dose modification visit

Every time a dose should be reduced or increased (refer to [Section 4.1.4](#) and [Section 4.2.1](#)) patients will need to come to the site for a dose modification visit where the following will be performed:

Proprietary confidential information.

© 2017 Boehringer Ingelheim International GmbH or one or more of its affiliated companies. All rights reserved.

This document may not - in full or in part - be passed on, reproduced, published or otherwise used without prior written permission.

- Physical examination measuring weight;
- Vital signs;
- Assessment of adverse events, acute exacerbations and concomitant therapy since last visit;
- PFT (FVC);
- Assignment of new dose in IVRS/IWRS;
- Dispensing of trial drug;
- Drug accountability.

6.2.5. Period after the database lock for the final analysis

After the database lock for the final analysis (refer to [section 7.3](#)) and once consent has been provided, the remaining patients in the trial (patients without access to nintedanib outside the clinical trial) will be offered continuation of treatment within the trial. This period will consist of study visits every 16 weeks (± 2 weeks) where the following procedures will be conducted:

- Assessment of adverse events and concomitant therapy since last visit;
- Dispensing of trial drug.

Patients will continue to receive treatment until they meet a reason for discontinuation (refer to [section 3.3.4](#)) or until access to nintedanib is obtained outside the clinical trial.

Dose reductions, interruptions and re-escalations are possible at any time during the scheduled study visits or between visits to manage adverse events.

End of treatment and follow up visits have to be performed to conclude the treatment period and trial participation.

Study procedures per visit are described in the [Flow Chart](#) for patients who continue treatment after the database lock for the final analysis. Investigators are encouraged to monitor liver function locally according to the recommendations provided in the Investigators Brochure.

Only Adverse Events, Concomitant medications and reason of trial drug discontinuation and trial completion will be collected in the eCRF.

Proprietary confidential information.

7. STATISTICAL METHODS AND DETERMINATION OF SAMPLE SIZE

7.1 STATISTICAL DESIGN - MODEL

This is a multicenter, multi-national, open-label clinical trial to investigate the long term safety of nintedanib in patients with IPF previously treated in a double-blind phase III placebo controlled trial (1199.32 or 1199.34).

This statistical paragraph deals with the analyses to be performed on the extension trial only. Although data of parent trial will not be described in the scope of these analyses, they will be taken into account for adverse events analyses, as described in [Section 7.3.4](#).

As the main objective of this extension trial is to study long-term safety, only descriptive statistics will be used.

7.2 NULL AND ALTERNATIVE HYPOTHESES

All analyses in this trial are descriptive and exploratory in nature. No formal statistical inferences are foreseen.

7.3 PLANNED ANALYSES

The treated set (TS) will consist of all patients who received at least one dose of open-label study medication.

The definition of important protocol violations (IPV) will be specified in the trial statistical analysis plan (TSAP). These IPV definitions will include consideration of important violations of entry criteria, treatment non-compliance, prohibited medications and inadequate follow-up of hepatic events.

Patients will be analysed according to their randomized treatment group in previous studies 1199.32/34, and overall.

The last available value between visit 1 and visit 2 (before first trial drug intake) will be considered as the baseline, for this extension trial.

The main statistical analyses as described below will be performed based on all data collected up to the third interim database lock date ([see section 7.4](#)). Afterwards, only adverse events and concomitant treatments listings will be provided.

7.3.1 Primary endpoint analyses

The primary objective of the study is to assess the safety of nintedanib, so please refer to [Section 7.3.4](#). Number of patients and % will be presented over the extension trial by

Proprietary confidential information.

[figure not shown]
© 2017 Boehringer Ingelheim International GmbH or one or more of its affiliated companies. All rights reserved.

This document may not - in full or in part - be passed on, reproduced, published or otherwise used without prior written permission.

category for adverse events overall; serious adverse events; adverse events leading to treatment discontinuation and fatal adverse events.

7.3.2 Secondary endpoint analyses

Not applicable

7.3.4 Safety analyses

The planned analysis is described in [section 7.3.1](#) and [7.3.3](#).

Proprietary confidential information.

© 2017 Boehringer Ingelheim International GmbH or one or more of its affiliated companies. All rights reserved.

This document may not - in full or in part - be passed on, reproduced, published or otherwise used without prior written permission.

All patients in the treated set will be included in the safety analysis. The analyses of adverse events will be descriptive in nature and will be based on BI standards. No hypothesis testing is planned.

Statistical analysis and reporting of adverse events will concentrate on treatment-emergent adverse events (in extension study), based on BI Guideline “Handling of Extension Trials”. To this end, all adverse events will be classified according to the following trial periods: previous trial, between-trials (from follow-up visit in previous trial up to date of informed consent in extension study), screening, on-treatment, post-treatment and post-study.

All adverse events with an onset date from the date of the first dose in the extension trial up to 28 days after the end of trial treatment will be assigned to the on-treatment period. Other adverse events will be assigned to the previous trial, between-trials, screening, post-treatment, or post-study period, as appropriate.

Frequency, severity, and causal relationship of adverse events will be tabulated by system organ class and preferred term after coding according to the current version of the Medical Dictionary for Drug Regulatory Activities (MedDRA).

7.3.5 Pharmacokinetic analyses

Not applicable.

7.4. INTERIM ANALYSES

A first interim analysis will be performed to include safety data from this study in the regulatory submission documents of nintedanib in IPF. The appropriate analyses will be detailed in the Trial Statistical Analysis Plan; the timing of the interim database lock will be defined to allow for presentation of the most complete data.

A second interim analysis will be performed after the last patient entered into the trial has reached 48 weeks of treatment.

A third statistical analysis will be performed allowing the final assessment of all endpoints of this trial (refer to [section 5.1](#)). This will be the basis of the final Clinical Trial Report.

All the above mentioned analyses in [Section 7.3](#) will be presented at each interim analysis.

Data collected after the third interim DBL date will only be listed once all patients have discontinued the trial and then incorporated in a revision of the CTR. Details will be provided in the TSAP.

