5. VARIABLES AND THEIR ASSESSMENT

5.1 TRIAL ENDPOINTS

5.1.1 Primary Endpoint

The primary endpoint is the incidence (number and % of patients) of overall adverse events over the course of the study, including incidence (number and % of patients) of serious adverse events; adverse events leading to discontinuation and fatal adverse events.

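### The primary adverse-event incidence is defined over the whole study but counted only to the third database lock; later events are listed and, in the visible text, never enter the counts

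*Protocol*

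**What the plan says.** **Endpoint.** Protocol 5.1.1: "The primary endpoint is the incidence (number and % of patients) of overall adverse events over the course of the study". It covers serious events, events leading to discontinuation and fatal events. For the analysis, 7.3.1 says: "Number of patients and % will be presented over the extension trial by" category. In 7.3.4, events from the first extension dose "up to 28 days after the end of trial treatment will be assigned to the on-treatment period", with no cut at a database lock.

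**Data cut.** Section 7.3 opens its analysis plan with: "The main statistical analyses as described below will be performed based on all data collected up to the third interim database lock date". It continues: "Afterwards, only adverse events and concomitant treatments listings will be provided". Section 7.4 adds: "A third statistical analysis will be performed allowing the final assessment of all endpoints of this trial", refers to section 5.1, and makes this analysis the basis of the final report. For what comes later: "Data collected after the third interim DBL date will only be listed once all patients have discontinued the trial". Those listings go into a revision of the report, with details left to the SAP.

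**After the cut.** Under 6.2.5, patients who cannot get nintedanib elsewhere may continue treatment within the trial. Adverse events, concomitant medication and reasons for stopping are still entered in the eCRF. Section 6.1 has the trial run until every patient has stopped treatment or a stopping criterion is met.

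**SAP.** Section 7.4 sends the primary question to the safety analyses in 7.8. Table 6.6.1:1 sets the cut-off for time-to-event endpoints at the interim database lock. The visible text has no rule for tabulating adverse events after the third lock.

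**The concern.** Amendment 3 created a treatment period that lies inside the trial, and so inside the endpoint's stated time frame, but outside the tabulation. The amendment put the cut-off into 7.3 and 7.4 and left the time frame in 5.1.1 and 7.3.1 as it was. A reader of the final report would take the primary percentages to cover the study when they cover it only to the third lock.

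The objective is long-term safety. A listing shows each later event but gives no count of patients and no percentage, which is the form in which the primary endpoint is defined. A later death or discontinuation for an adverse event would be in the report and not in the primary result.

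**Working it through.** The plan states no figure to reproduce: 7.7 gives no sample-size calculation and 7.2 makes all analyses descriptive. The check is textual, followed by an illustration of size.

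**Step 1. Time frames side by side**

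| Item | Period covered | Protocol section |
|---|---|---|
| Endpoint definition | Whole study | 5.1.1 |
| Primary analysis | Extension trial | 7.3.1 |
| On-treatment window | First dose to 28 days after end of treatment | 7.3.4 |
| Treatment and event collection | Continue after the lock | 6.2.5 |
| Main analyses | To the third lock | 7.3 |
| Later data | Listings only | 7.3, 7.4 |

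The first four rows extend past the lock and the last two stop the counting there.

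**Step 2. Which counts can change**

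- *Fatal, and leading to discontinuation.* A patient still on drug at the lock has not died and has not permanently stopped for an adverse event. Any such patient with a later event would be a new count.
- *Serious.* Only a patient's first serious event adds to the count.
- *Any event.* Only patients with no event by the lock can add. After long treatment these are probably few.

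**Step 3. Illustration**

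Only N = 750 is from the documents (planned number, synopsis and 3.1). The rest is assumed: K patients continue, a share r of them have an event of the given type after the lock, and a share s are already counted for that category.

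Fatal, or leading to discontinuation: patients added = K × r; percentage points = 100 × K × r / N.

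| K | r = 10% | r = 20% | r = 40% |
|---|---|---|---|
| 10 | 1 (0.13) | 2 (0.27) | 4 (0.53) |
| 50 | 5 (0.67) | 10 (1.33) | 20 (2.67) |
| 150 | 15 (2.0) | 30 (4.0) | 60 (8.0) |

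Cells show patients (percentage points).

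Serious: points = 100 × K × (1 − s) × r / N. With K = 50 and r = 20%:
- s = 30%: 50 × 0.7 × 0.2 = 7 patients, 0.93 points
- s = 80%: 50 × 0.2 × 0.2 = 2 patients, 0.27 points

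Any event: with s = 95%, at most 100 × K × 0.05 / N.
- K = 10: 0.07 points
- K = 50: 0.33 points
- K = 150: 1.0 point

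Chance that at least one fatal event falls outside the table, 1 − (1 − r)^K:
- K = 50: 92% at r = 5%, 99.5% at r = 10%
- K = 10: 40% at r = 5%, 65% at r = 10%

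**The case against.** The strongest reply is that the cut is open and deliberate. The sentence at the head of 7.3 governs 7.3.1 beneath it, and 7.4 calls the third analysis the final assessment of the endpoints in 5.1. The endpoint is therefore computed, on all data to the lock. Later events are collected, listed and reported, and with no hypothesis test no inference is biased. All of this stands. A reader might infer that the endpoint goes uncomputed, that the analysis text was not amended, or that late events are lost. The documents support none of these. What remains is that 5.1.1 and 7.3.1 still state a longer period than the one counted.

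A second reply is that the period after the lock is different in kind, so listing it separately is defensible. The post-lock flow chart drops laboratory tests, physical examination, vital signs and FVC, while 5.3.6.1 records clinically relevant changes in laboratory results, vital signs and examination as adverse events. Ascertainment is therefore less complete. This also stands and argues for showing the all-data result beside the third-lock result rather than in its place. The visit interval is not the difference: after week 48, visits that collect adverse events are every 16 weeks both before and after the lock, and the intermediate visits before it are for liver tests only.

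Third, 7.4 leaves details to the SAP, and section 9.2, which its introduction cites for interim outputs, was not in the text available. A rule there cannot be excluded.

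**Conclusion.** The mismatch is real and minor. The primary endpoint's stated period runs past the third lock, its counts do not, and no visible text closes the gap. The effect is greatest for fatal events and events leading to discontinuation, smaller for serious events, and slight for any event.

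Its size is unknown because the documents do not say how many patients continue or for how long. The central illustration, 10 patients or 1.3 points of 750, rests on assumed values (50 continuing, 20% with an event). Across the assumed ranges the addition runs from 1 to 60 patients, or 0.13 to 8.0 points.

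A reader might also infer that the plan sets aside the longest-exposed patients. The documents do not say that. Patients continue because they lack outside access to the drug, and equally exposed patients in countries with access leave when the trial ends there. Those who continue will go on accruing exposure, but they are not selected for it. Patient-years after the lock would not measure the effect either, since the endpoint counts patients and many may already be counted.

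**What to change.** 1. In Protocol 5.1.1 and 7.3.1, and on the table itself, label the third-lock result *up to the third database lock*.
2. In the report revision already planned under 7.4, show the number and percentage of patients in the four categories (any, serious, leading to discontinuation, fatal) on all data to last patient out, beside the third-lock result. Listings can remain for everything else.
3. Footnote the all-data column: after the lock, protocol laboratory tests, physical examination, vital signs and FVC are no longer done, so events found through them are less fully ascertained, and the continuing patients are only those without outside access to nintedanib.

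The cost is a wording change and one re-run of a small descriptive table. The data needed are already collected: 5.3.7 requires seriousness, outcome and action taken for each event, and 6.2.5 keeps adverse events and reasons for stopping in the eCRF. With no hypothesis test, a second data cut raises no multiplicity question. If SAP section 9.2 already provides such a table, only the labelling is needed.
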